- To determine changes in the respiratory microbiome after inhibition of IL-4R α in patients with asthma at 1 and 4 months after initiation of treatment

Primary Endpoint (Biological) Measures

- Changes in measured features of respiratory microbiota composition (bacteria, fungi), profiled from induced sputum and nasal samples. Such features include alpha- and beta-diversity ecologic measures, which reflect microbiota composition within and between-samples, respectively. Examples include Shannon and phylogenetic diversity indices, richness and evenness metrics (alpha-diversity), and Unifrac or Bray-Curtis distance measures to compare across samples (beta-diversity). Additional readouts of the microbiome to be analyzed include bacterial burden by quantitative PCR, abundance profiles of microbial community members, and microbial gene functions annotated from metagenomic sequence data.
- Changes in similarly calculated measures of microbiota composition in stool samples collected before and after dupilumab initiation (baseline and 4 months)

Secondary Objectives

- To examine correlations between changes in measured features of the respiratory microbiome and changes in blood and airway immune responses with dupilumab treatment
- To determine relationships between changes in measured features of the respiratory microbiome and changes in clinical outcome measures including lung function and asthma control scores with dupilumab treatment
- To determine if combinations of correlated immune markers and microbiota patterns predict improvement or lack of improvement in clinical outcome measures related to dupilumab treatment
- To explore associations between gut microbiome composition, aeroallergen sensitization, severe asthma features and response to dupilumab treatment.
- To explore the relationship between gut microbiota compositional, the intestinal metabolome, and response to dupilumab.
- To explore and compare dupilumab-related, compartment-specific changes in the respiratory microbiome to that observed in the gut microbiome

Secondary Endpoint (Clinical) Measures

Clinical outcome measures (all visits)

- Spirometry: FEV1/FVC ratio, FEV1, and FVC pre- and post-bronchodilator.
- Fractional exhaled nitric oxide (FeNO)
- Asthma Control Test [16]
- Asthma quality of life questionnaire (mini-AQLQ) [17]
- SNOT-22 [18, 19]
- Asthma medication use and dosage
- Asthma exacerbations requiring at least 3 days of oral corticosteroids

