Dupilumab-eligible severe asthma patients will be identified and recruited from asthma and allergy clinics at the University of Michigan. Severe asthma patients are seen and cared for by Pulmonary and Allergy faculty at two main outpatient clinic locations. All severe asthma patients who meet clinical prescribing criteria for dupilumab are considered eligible and will be recruited for this study. The study coordinator and/or physician investigator will meet with subjects to provide information about the study and invite them to participate in this 3-visit study occurring over a 4-month period. We will enroll 15 severe asthma patients who complete all 3 visits. The funder of the grant for this project (Regeneron) will provide dupilumab for this study.

Inclusion criteria:

1. Adults ages 18 or older with physician-diagnosed/-managed severe asthma who are clinically eligible for dupilumab (clinical criteria below).
2. Current treatment with a medium-to-high-dose inhaled glucocorticoid (fluticasone propionate at a total daily dose of ≥ 440 μ g or equipotent equivalent) plus up to at least one additional controller (e.g., a long-acting β 2-agonist or leukotriene receptor antagonist)
3. Eosinophilic asthma phenotype (blood eosinophil level >300) or asthma requiring daily oral corticosteroids
4. Asthma that is uncontrolled, as defined by a score on the Asthma Control Test of 19 or lower, OR a worsening of asthma in the past year that led to an asthma hospitalization, ED visit, or 3 days of oral corticosteroids
5. Severity of asthma that, in the opinion of the subject's asthma care specialist, requires dupilumab for control

Exclusion Criteria:

1. Patients with diagnosis of other chronic lung diseases (e.g. COPD, idiopathic pulmonary fibrosis, Churg-Strauss syndrome, ABPA, etc.)

2. Current smoker or reported smoking within 1 month of the screening visit (tobacco or any inhaled recreational product)
3. Greater than 10 total pack-year of cigarette smoking history
4. Treatment with oral corticosteroids for an asthma exacerbation 1 month prior to screening or during the screening period
5. Use of any biologic therapy for asthma within the past 3 months
6. Respiratory or GI illness within 1 month prior to screening or during the screening period
7. Treatment with antibiotics for acute infections within six weeks prior to screening or during the screening period.
8. Pregnancy at enrollment or during the study
9. Known hypersensitivity to dupilumab or its excipients

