This is a pilot, proof-of-concept study. There is no available published data (at the time of writing) that addresses the same research questions to perform a sample size calculation based on changes in microbiome readouts (primary objective/endpoint) related to dupilumab intervention. However, we have previously reported significant changes in the airway microbiome, related to a prospective treatment intervention (fluticasone propionate), in comparisons that also involved small numbers of subjects. Specifically, in an earlier NHLBI AsthmaNet Proof-of-concept study, we examined the effects of randomized, placebo-controlled fluticasone intervention (6 weeks) on the airway microbiome in subjects with mild asthma. We identified fluticasone-associated changes in the airway microbiome between steroid-responders vs. non-responders, in an initial analysis of paired protected bronchial brushings from 16 subjects [13]. In an analysis of induced sputum from the same study, we recently reported changes in the airway microbiome related to fluticasone intervention, which differed from placebo [14]. Notably, we observed a significantly greater change in airway microbial community structure in ICS non-responders (n=8) compared to responders (n=12).

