For Hypothesis 2, we will compare alpha-diversity measures before and after treatment (baseline vs month 1; baseline vs. month 4; all three timepoints), using paired t-test, Wilcoxon sign-rank test or rm-ANOVA. For beta-diversity -based measures of overall microbial composition, we will use Bray-Curtis or Unifrac distance matrices to perform (i) pairwise PERMANOVA tests (R package vegan; adonis2 or in QIIME2 (q2-longitudinal) [20,21]; (ii) linear mixed-effects models with a random intercept and slope for each individual; (iii) Procrustes analysis with Mantel test. We will also explore other available tools for time-series microbiome analysis such as MDSINE [22]. Differences in specific species (ASVs, OTUs) between time points will be analyzed using DESeq2 which applies a variance-stabilizing transformation to the data. Other methods using log-ratio transformation (e.g., CLR) of species counts will also be explored.

For Hypothesis 3, we will examine correlations between change in biomarkers (e.g., cytokines, inflammatory cell counts, targeted gene expression) and changes in the airway or gut microbiome. The latter based on either specific compositional readouts (ASV, OTUs) or in terms of overall microbial community structure. The following approaches will be used: (i) initial correlation analyses performed between paired data at each time point (e.g., specific biomarker dataset vs. microbial ASVs), using Spearman correlations, with adjustments for multiple comparisons by q-values; (ii) linear mixed-effects models, e.g. levels of immune markers as predictors of post-treatment microbiota diversity or abundances of each microbiota member; fixed effects would include age, sex, BMI, and chronic treatments including corticosteroids or macrolides (type, dose, route); (iii) tests for biomarker association with overall microbial community structure, using distance-based PERMANOVA (adonis2) at each time point or in a paired design; (iv) additional computational approaches based on methods for high-dimensional dataset comparisons, as described below.

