For Hypothesis 4, which focuses on microbial correlations with clinical outcome measures rather than biomarkers, we will apply same approaches as described for Hypothesis 3. In addition, we will explore the following analysis methods (also applicable to Hypothesis 3): (i) feature-volatility action algorithm, which performs longitudinal feature selection based on random forest regression, implemented in q2-longitudinal in QIIME2; (ii) tools in the R mixOMICS package which bundles access to several sparse multivariate modeling methods that aim to identify key features that explain a biological or clinical outcome of interest.

Related to this, and to leverage tools for examining microbiome data with other -omics/high-dimensional data we will apply tools such as DIABLO (available in mixOMICS package). DIABLO performs data integration coupled with discriminant analysis approach to identify combinatorial features predictive of a binary outcome (e.g., is there a combination of microbial and metabolite features that predict improved asthma control or not? or that associate with an immune biomarker of interest?) As an example, we have recently used DIABLO to explore microbial and metabolite features associated with COPD outcome measures in a multicenter study. In addition, we will determine co-occurrence relationships between microbiota (SparCC [24] or SPIEC-EASI [25]) to identify highly correlated species and determine if 'hubs' of microbiota associate with particular cytokines or metabolites, following by analysis for clustering patterns of microbial-immune relationships [26]. Given the likely heterogeneity of measures in the molecular data types and the small number of subjects, we will apply corrections for multiple comparisons where indicated.

References

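### The Hypothesis 3 and 4 mixed models carry an open list of about 4 to 9 covariates for 15 patients, yet omit the baseline value of the microbiota outcome and do not date the steroid terms

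*Combined protocol and SAP*

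**What the plan says.** Section IV sets the sample: "We will enroll 15 severe asthma patients who complete all 3 visits". Section XII gives no power basis for that number: "There is no available published data (at the time of writing) that addresses the same research questions to perform a sample size calculation".

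For Hypothesis 3, Section XII lists four approaches. Approach (ii) is a linear mixed-effects model, illustrated by "levels of immune markers as predictors of post-treatment microbiota diversity or abundances of each microbiota member", and the "fixed effects would include age, sex, BMI, and chronic treatments including corticosteroids or macrolides (type, dose, route"). The plan gives no coding of the treatment terms, no visit at which they are taken, no ranking of covariates and no upper limit on their number. For Hypothesis 4 the plan states "we will apply same approaches as described for Hypothesis 3".

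The number of measurements differs by compartment. The primary objective for the airway is "To determine changes in the respiratory microbiome after inhibition of IL-4R α in patients with asthma at 1 and 4 months after initiation of treatment", so there are two post-treatment values. The stool endpoint is "Changes in similarly calculated measures of microbiota composition in stool samples collected before and after dupilumab initiation (baseline and 4 months"), so there is one. Table 1 repeats NELF, sputum and blood count at V1, V2 and V3 but takes total and specific IgE at V1 only. Section III lists asthma medication use and dosage among the clinical outcome measures at all visits.

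**The concern.** Three features of approach (ii) fit the stated question poorly.

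1. **Target.** Hypothesis 3 relates changes in biomarkers to changes in the microbiome. The example regresses a post-treatment value on marker levels. The V1 value of the same outcome would turn that into a statement about change, and it is not listed.
2. **Timing of treatment terms.** If corticosteroid dose is taken at follow-up, the model conditions on something the protocol itself treats as an outcome. Part of the response under study could then be adjusted away.
3. **Length of the list.** Age and sex are fixed, and BMI moves little in four months. Such terms spend between-patient degrees of freedom, of which there are few. With type, dose and route left uncoded, the marker coefficient can also depend on coding choices made after the data are seen.

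At stake is whether the adjusted estimates are stable enough to carry forward from a pilot, chiefly for the gut outcomes and the baseline-only markers.

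**Working it through.** **Inputs from the documents.** 15 patients (Section IV); the covariate list (Section XII); two post-treatment airway values and one stool value (Section III); IgE at V1 only (Table 1).

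**Assumptions, because the documents give none.** Two-sided level 0.05 before multiplicity; true partial correlation 0.5, with 0.3 as a lower case; covariates unrelated to the marker. There is no planned power figure to reproduce.

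**Counting terms.** Age, sex and BMI make 3.
- One coarse treatment term: 3 + 1 = 4.
- Steroid type, dose and route plus one macrolide term: 3 + 3 + 1 = 7.
- Three macrolide terms instead of one: 3 + 3 + 3 = 9.

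The plan states no count; 4 to 9 is the range its wording allows.

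**One value per patient.** With k covariates, an intercept and the marker, residual df = 15 − k − 2. The smallest significant partial correlation is r = t / √(df + t²), where t is the 97.5th percentile of the t distribution. For k = 0, t = 2.160 and r = 2.160 / √(13 + 4.67) = 0.514. For k = 9, t = 2.776 and r = 2.776 / √(4 + 7.71) = 0.811. Power is from at least 200,000 simulated data sets per cell.

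| k | Residual df | Critical r | Power at r = 0.3 | Power at r = 0.5 |
|---|---|---|---|---|
| 0 | 13 | 0.51 | 19% | 50% |
| 2 | 11 | 0.55 | 17% | 44% |
| 4 | 9 | 0.60 | 15% | 36% |
| 7 | 6 | 0.71 | 11% | 25% |
| 9 | 4 | 0.81 | 8.5% | 17% |

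Cross-check by Fisher's z at r = 0.5: atanh(0.5) = 0.549, multiplied by √(15 − k − 3), compared with 1.96.
- k = 0: 0.549 × 3.464 = 1.903, power 48%.
- k = 2: 0.549 × 3.162 = 1.737, power 41%.
- k = 7: 0.549 × 2.236 = 1.228, power 23%.
- k = 9: 0.549 × 1.732 = 0.951, power 16%.

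These agree with the simulation to within about 3 points. The share of the 13 df used is 4/13 = 31%, 7/13 = 54% and 9/13 = 69% for k = 4, 7 and 9.

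**Marker and outcome repeated over visits.** A random-intercept model was simulated with 15 patients, visit effects, residual outcome intraclass correlation 0.5, equal between- and within-patient slopes, and the critical value calibrated to 5% under the null (1,500 simulations per cell). Power at r = 0.5, from k = 0 to k = 8:

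| Marker intraclass correlation (assumed) | Two visits | Three visits |
|---|---|---|
| 0.3 | 85% to 69% | 96% to 94% |
| 0.6 | 73% to 56% | 92% to 83% |
| 0.9 | 69% to 36% | 71% to 47% |

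Patient-level covariates cost between-patient information only. A marker that varies across visits keeps its within-patient information; a stable marker behaves more like the single-value case.

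**The case against.** The strongest reply is that the single-value figures describe only part of the plan. Approach (ii) specifies mixed models, and most airway and blood markers are repeated. With 8 covariates the simulated power at r = 0.5 is 36% to 69% over two visits and 47% to 94% over three. A reader might infer that a moderate marker–microbiome link is very unlikely to be found in any of these models. That does not follow; the low figures belong to stool outcomes and V1-only markers.

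A reader might also infer that Hypotheses 3 and 4 rest on approach (ii). They do not. Section XII also plans Spearman correlations "with adjustments for multiple comparisons by q-values", with no covariates stated, as well as PERMANOVA and multivariate methods. The model is introduced as an example, in a study whose hypotheses are called exploratory.

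Other parts of the reply also stand. All patients take inhaled corticosteroid by inclusion criterion, and the documents do not say that any will take a macrolide, so the realised list may be near 4. Sample size limits power even with no covariates: 50% at r = 0.5 and 19% at r = 0.3. Fixed traits can still confound a between-patient association, so adjusting for them is not pointless.

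The reply does not answer the missing baseline value, the undated steroid terms or the absence of any limit on the list. Section XII acknowledges the small number of subjects but responds only with multiplicity correction, which does not address overfitting.

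**Conclusion.** The point holds in a limited form. The covariate list is open and unranked for 15 patients, leaves out the V1 value of the outcome, and does not date treatment terms that the protocol also counts as outcomes. For single-value models the cost at r = 0.5 is a fall in power from 50% to about 36% (4 terms), 25% (7) or 17% (9), before multiplicity. For repeated markers the loss is smaller, and its size depends on an intraclass correlation that the documents do not give.

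The figures assume covariates that are unrelated to the marker and explain none of the outcome. Strongly prognostic covariates would reduce the loss; covariates correlated with the marker would increase it. The omissions of baseline value and visit do not depend on any power figure.

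**What to change.** In approach (ii), for post-treatment microbiota outcomes:

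- Make the main model the marker, the V1 value of the same outcome, and at most one further prespecified term taken at V1 (for example daily oral corticosteroid, yes/no).
- Add visit and a patient random intercept only where there are two or more post-treatment values. Use ordinary linear regression for stool, because with one post-treatment value a patient intercept cannot be separated from residual error.
- Put age, sex, BMI and the other treatment terms, all at V1 values, in sensitivity models one at a time.
- Apply the same rule to the Hypothesis 4 models.

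With two covariates, a single-value model keeps 11 residual df and about 44% power at r = 0.5, before any gain from the baseline value explaining outcome variance.

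The cost is wording only, since the V1 samples are already scheduled. The small downside is that between-patient confounding is then examined in sensitivity models, not in the main model.

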Appendix 1. Asthma Control Test (ACT)

The Asthma Control Test (ACT) is a patient self-administered tool for identifying those with poorly controlled asthma. It is based on a 4-week recall of symptoms and daily functioning captured in 5 items on the questionnaire. These include assessment of the frequency of shortness of breath, general asthma symptoms, use of rescue medications, the effect of asthma on daily functioning, and overall self-assessment of asthma control. Each item is scored on a 5-point scale, with higher scale values indicative of, depending on the question, infrequent/absent symptoms or better asthma control.

The ACT score is the sum of the values for all 5 items. The scores range from 5 (poor control of asthma) to 25 (complete control of asthma), with higher scores reflecting greater asthma control.

An ACT score >19 indicates well-controlled asthma; the minimal clinically important difference in score is 3.

Appendix 2. Mini-Asthma Quality of Life Questionnaire Control (mAQLQ)

The shorter and simpler mAQLQ consists of 15 questions and was developed to meet the need for greater efficiency in large clinical trials and group patient monitoring. The mAQLQ is a patient self-administered test with questions covering 4 domains: Symptoms (5 questions), Activity Limitations (4 questions), Emotional Function (3 questions), and Environmental Stimuli (3 questions). The recall time for the mAQLQ is 2 weeks, so patients must base their answers on their experiences during the previous 2 weeks.

To score the mAQLQ, there is an overall score and a mean score for each domain.

Overall score (average of 15 questions): add up responses to all questions, and divide by 15.

Mean for each domain: add up responses to each item and take the average for each domain.

Symptoms: items 1, 4, 6, 8, 10 (sum & divide by 5; variable label- mAQLQ-S)

Activity Limitations: items 12, 13, 14, 15 (sum & divide by 4; variable label- mAQLQ-AL)

Emotional Function: items 3, 5, 9 (sum & divide by 3; variable label- mAQLQ-EF)

Environmental Stimuli: items 2, 7, 11 (sum & divide by 3; variable label- mAQLQ-ES)

Appendix 3. SNOT-22 Questionnaire.

Appendix 4. Nasal Epithelial Lining Fluid (NELF) collection (diagram, instructions).

Appendix 5. Stool Collection Instructions.
